Patients will be randomized to receive either methadone 0.2mg/kg (maximum dose 20mg) or equipotent dose of morphine, adding to a syringe containing saline made up to 50ml in total, by drawing sequentially numbered, coded sealed, opaque envelopes each containing the group assignment of either methadone or morphine group. The sealed envelopes for randomization will be prepared by a third party who takes no further part in the study. The study syringes containing the drug solution will be prepared by a nurse not involved in the study with blind labelling. The primary care team, blinded to the group allocation, will perform all surgical procedures using standardized techniques. Anaesthetists and nurses blinded to group allocation will record data intraoperatively, in ICU, and at regular intervals in the cardiac wards.

Eligibility criteria

We will include adult patients age 18 or older, undergoing elective coronary artery bypass graft (CABG), valve repair/replacement, or combined CABG valve procedure via sternotomy, with an expected extubation within 12 hours of surgery. The exclusion criteria include emergency surgery, aortic surgery, redo surgery, preoperative renal failure requiring renal replacement therapy or creatinine clearance <30ml/min (calculated by Cockcroft-Gault formula), liver dysfunction (liver enzymes twice upper limit normal), LVEF <40%, requirement of mechanical hemodynamic support in perioperative period, history of chronic pain or who regularly used pain medications (except paracetamol and non-steroidal anti-inflammatory drugs), history of psychiatric illnesses or illicit drug use, intraoperative use of remifentanil and unable to provide informed consent.

Anaesthesia and interventions

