All patients will receive standard monitoring for cardiac surgery. General anaesthesia will be induced with midazolam 0.01-0.05mg/kg, fentanyl 2-5mcg/kg and rocuronium 0.5-1mg/kg to facilitate intubation with single-lumen cuffed endotracheal tube. Anaesthesia will be maintained with sevoflurane and propofol infusion that target Bispectral Index 40-60. The study drug (either methadone 0.2mg/kg or morphine at equipotent dose) in blind labelling will be administered at time of induction by intravenous infusion over 30 minutes. No further morphine will be given throughout the operation. No other analgesics (paracetamol, non-steroidal anti-inflammatory agents, dexmedetomidine, ketamine), steroids or antiemetics will be given intraoperatively. Patient-controlled analgesia (PCA) morphine protocol will be prescribed to patients for 72 hours after operation for postoperative analgesia. Oral analgesics including paracetamol 1g every 6 hours and dihydrocodeine 30mg three times a day will be prescribed by parent surgical team. At the end of the operation, the patients will be kept sedated with propofol infusion to ICU. Propofol infusion will be stopped upon admission to ICU to facilitate weaning from ventilator. Adaptive Support Ventilation (ASV) is used in ICU for weaning which adjusts the ventilation parameters depending on the patient's lung mechanics and effort. Pain will be assessed by nurses in ICU at 4h after stopping sedation, then once every 2h. Upon extubation, patient will be assessed the pain score and the level of sedation at 15min, 8h, 12h, 24h, 48h and 72h. 1mg morphine will be administered via PCA to patients if pain of more than mild severity was noted. Any nausea or vomiting, and use of rescue antiemetics will be documented.

Outcome measures

Primary outcomes

The most intense pain typically occurs in the first 2-3 days after open heart surgery, leading to greater need for analgesia during this period. The primary outcome will be set at 72-hour time frame based on the postoperative morphine consumption.

Secondary outcomes

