The sample size is calculated using G*Power software version 3.1.9.3 (Kiel University, Kiel, Germany), and based on postoperative morphine consumption at 24 hours, which is the primary outcome variable. Because there was no randomized controlled trial on use of methadone in cardiac surgery in Asian population, a pilot study (50 patients) was conducted from cardiac surgical patients in Prince of Wales Hospital, Hong Kong. The mean (SD) postoperative morphine consumption at 24 hours was 21.5 (8.2) mg in patients receiving methadone, whereas that for morphine group was 30.3 (14.0) mg. With an alpha probability of 0.05 and a power of 90%, a sample size of 34 patients in each group will be needed. Assuming 15% drop-out rate, the sample size is increased to 86 patients. The primary analyses will be performed on a modified intention-to-treat basis. Patients will be analysed according to their randomized allocated groups but will be excluded from the analysis if they do not adhere to the protocol after randomisation. Categorical data are reported as numbers and percentages. Continuous variables are reported as mean (standard deviation) or median (interquartile range) as appropriate after checking for normality using the Shapiro-Wilk's test. Comparison of continuous data is performed by Student's *t* test and by Mann-Whitney U test for non-normally distributed data. Chi-square test is used to compare groups with categorical variables. Level of significance is set at P<0.05. SPSS 27.0 software (IBM Corp, Armonk, NY) will be used for data analysis.

DECLARATIONS

Consent to participate

All participants will provide written informed consent. All research will be conducted in accordance with the Declaration of Helsinki and all other relevant guidelines and regulations.

Consent for publication

Not applicable

Competing interests

The authors declare that they have no competing interests.

Funding

This work was funded by the Health and Medical Research Fund from the Health Bureau of the Government of HKSAR (Reference number: 10211156), and internally supported by the Department of Anaesthesia and Intensive Care, The Chinese University of Hong Kong. This funding has no role in the design of this study and will not have any role during its execution, analyses, interpretation of the data, or decision to submit results.

REFERENCES

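### The primary analysis set drops any randomised patient who later departs from the protocol, so it is in effect a per-protocol set under a modified intention-to-treat label

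*Protocol*

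**What the plan says.** Under *Sample size calculation and statistical methods* the protocol states: "The primary analyses will be performed on a modified intention-to-treat basis". The next sentence keeps patients in their allocated groups but adds that they "will be excluded from the analysis if they do not adhere to the protocol after randomisation". It does not say which deviations count, how serious they must be, when they must occur or who decides. The protocol names no other analysis set.

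Under *Anaesthesia and interventions* the study drug "in blind labelling will be administered at time of induction by intravenous infusion over 30 minutes". The same section then sets conditions that can be broken only during or after that infusion:

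- "No further morphine will be given throughout the operation";
- a ban on other intraoperative analgesics, steroids and antiemetics;
- postoperative analgesia, where a patient-controlled (PCA) "morphine protocol will be prescribed to patients for 72 hours after operation for postoperative analgesia".

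Under *Primary outcomes*: "The primary outcome will be set at 72-hour time frame based on the postoperative morphine consumption".

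**The concern.** Modified intention-to-treat has no single definition, and the protocol states its rule openly, so the label alone is not the fault. The fault is the rule. Grouping patients as allocated and then removing those who did not adhere is what a per-protocol analysis does, and here it is the primary analysis.

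The rule conditions the primary comparison on events that follow randomisation and can follow from the drug. Extra intraoperative analgesia may mark a patient who will need more morphine, or may lower later need. The PCA regimen covers the same 72 hours as the primary outcome. If stopping PCA early, or receiving morphine outside it, were counted as non-adherence, a patient could be removed because of consumption itself.

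If exclusion is related to consumption and acts differently in the two arms, the result no longer estimates the effect of assignment. Methadone could look better or worse than it is. With no limits stated, exclusions could also be settled patient by patient after outcomes are known.

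**Working it through.** **The plan's own figure.** The inputs are in *Sample size calculation and statistical methods*: 24 h morphine 21.5 (SD 8.2) mg on methadone and 30.3 (SD 14.0) mg on morphine, alpha 0.05 (taken as two-sided), power 90%, drop-out 15%.

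- Difference: 30.3 − 21.5 = 8.8 mg.
- Pooled SD: √((8.2² + 14.0²)/2) = 11.47 mg; standardised difference 8.8/11.47 = 0.767.
- Normal approximation: 36 per group; 36/0.85 = 42.4, so 43 per group and 86 in total. This matches the stated total. (The stated 34 per group would give 34/0.85 = 40 per group, or 80; that is a separate matter and is not used here.)
- t-test power with all 43 per arm analysed is 94.0%; with 15% removed at random it is 89.9%. Loss of power is therefore not the main problem.

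**Model for selective exclusion.** Exclusion rates and correlations are assumptions; the documents give none. Each patient has a latent exclusion score with correlation ρ to morphine consumption, and is excluded if the score lies in the top fraction p. The mean of those kept then shifts by

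−SD × ρ × h(p), where h(p) = φ(z₁₋ₚ)/(1 − p).

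| p | 0.05 | 0.10 | 0.12 | 0.15 | 0.18 | 0.20 | 0.25 |
|---|---|---|---|---|---|---|---|
| h(p) | 0.109 | 0.195 | 0.227 | 0.274 | 0.320 | 0.350 | 0.424 |

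**No true effect, SD 11.47 mg in both arms.** False difference = 11.47 × |ρ| × (h(p₂) − h(p₁)). For 10% v 20% at |ρ| = 0.3: 11.47 × 0.3 × 0.155 = 0.53 mg. Type I error is from simulation of Student's t test, 43 randomised per arm, 100,000 runs per case.

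| Excluded | False difference, ρ of size 0.3 / 0.5 | Type I error, ρ of size 0.3 / 0.5 |
|---|---|---|
| Equal (10% or 15% in each arm) | 0 / 0 mg | 5.0 to 5.1% |
| 12% v 18% | 0.32 / 0.53 mg | 5.1 to 5.2% / 5.4% |
| 10% v 20% | 0.53 / 0.89 mg | 5.4% / 6.2 to 6.3% |
| 5% v 25% | 1.08 / 1.81 mg | 6.7 to 7.0% / 10.3 to 10.5% |

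At ρ = 0.1 even 5% v 25% gives only 5.1%.

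**Planned effect present, pilot SDs by arm.** Expected difference (morphine minus methadone) = 8.8 − ρ × (14.0 × h(p, morphine) − 8.2 × h(p, methadone)).

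- Methadone 10%, morphine 20%: the bracket is 14.0 × 0.350 − 8.2 × 0.195 = 3.30. The difference becomes 7.81 mg (ρ = +0.3), 7.15 (+0.5), 9.79 (−0.3) or 10.45 (−0.5). Simulated power (60,000 runs) is 83%, 79%, 95% and 98% in that order, against 90% at ρ = 0.
- Methadone 20%, morphine 10%: 8.73 to 8.87 mg, almost no change.
- 15% in each arm: the bracket is (14.0 − 8.2) × 0.274 = 1.59, so 8.00 mg at ρ = +0.5 and 9.60 mg at ρ = −0.5. Because the pilot SDs differ, equal exclusion is not neutral once there is an effect.

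All figures in mg are for 24 h. The protocol gives no mean or SD for the 72 h outcome.

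**The case against.** Five points can be made in the plan's defence.

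- **Blinding and a single dose.** *Randomization and concealment* has "The primary care team, blinded to the group allocation", and *Data collection* blinds the data collectors. One infusion at induction cannot be stopped or switched later, both arms receive an active opioid, and fentanyl and the depth-of-anaesthesia target are common to both. This stands in part. It prevents exclusions made knowing the arm and makes differential exclusion less likely, but it does not prevent exclusions that result from the drug's effect.
- **The PCA example is only one reading.** Prescribing PCA is a duty on the prescriber; a patient who uses little has not failed to adhere, and the protocol does not expressly forbid postoperative morphine outside PCA. This is fair: the example shows what the sentence permits, not what it requires. The intraoperative conditions do not depend on it.
- **The sentence may be aimed at a narrower group.** *Eligibility criteria* lists perioperative mechanical support and intraoperative remifentanil, which may become known only after allocation. That may be the intention, but the text does not confine the rule to them.
- **Such detail belongs in a statistical analysis plan.** This is true of classifying deviations and of sensitivity analyses. It is not true of the primary set, which the protocol itself fixes; a later plan would have to contradict this sentence to repair it.
- **The illustrated bias is small.** In most cases it is. Type I error of about 7 to 10% needs a fivefold imbalance in exclusions and a correlation of 0.3 to 0.5 in size.

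**Conclusion.** The concern holds. The only primary set that the protocol names excludes randomised patients on the basis of adherence after randomisation, without limit, and so is in effect a per-protocol set. This must be corrected, because it governs the headline comparison.

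That judgement rests on the principle and not on a predicted size. Under the assumptions shown, the bias runs from nothing (equal exclusion with no effect and equal SDs) through 0.3 to 0.9 mg in the middle cases to 1.8 mg in the most unbalanced one. With the planned effect present, the 8.8 mg could appear as anything from 7.15 to 10.45 mg. The sign of the correlation and the arm with more exclusions decide which way it goes, and the document settles neither.

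**What to change.** In *Sample size calculation and statistical methods*, define the primary set as all randomised patients who received any study drug and underwent surgery, analysed as allocated regardless of later protocol deviations. Keep the adherent patients as a per-protocol sensitivity analysis. Have deviations classified before unblinding by staff unaware of allocation, and report them by arm and reason afterwards. Also state whether patients who meet a perioperative exclusion criterion after dosing remain in the primary set; on this the protocol is silent rather than contradictory.

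No new data collection is needed, since *Data collection* already extracts 24 h and 72 h morphine totals from charts. Patients kept in whose 72 h consumption is absent or hard to compare, for example after death or prolonged ventilation, will need a stated handling rule.

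The statistical cost is dilution. Suppose that those who deviate show no effect at all (24 h figures, SD 11.47 mg, 43 per arm):

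- 10% deviate: 0.90 × 8.8 = 7.92 mg, power 88.6%, against 91.5% for an unbiased adherent set of 38.7 per arm.
- 15% deviate: 0.85 × 8.8 = 7.48 mg, power 84.8%, against 89.9% for 36.55 per arm.

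Analgesics given outside the protocol may also alter the consumption of patients who are kept; the sensitivity analysis would show how much that matters.

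### The protocol names the pooled-variance t test although its own pilot SDs are 8.2 and 14.0 mg; this is harmless with equal analysed groups but can mis-calibrate the P value if they become unequal (minor)

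*Protocol*

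**What the plan says.** All statements are in the protocol.

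- **Test** (Sample size calculation and statistical methods): "Comparison of continuous data is performed by Student's *t* test", with the Mann-Whitney U test for data that are not normal. Normality is judged by the Shapiro-Wilk test. The section mentions neither a check of variances nor an unequal-variance version of the t test.
- **Spread** (same section): a pilot of 50 patients gave 24-hour morphine consumption, as mean (SD), of "21.5 (8.2) mg in patients receiving methadone, whereas that for morphine group was 30.3 (14.0) mg".
- **Analysed groups** (same section): 34 per group are planned, raised to 86 in total for drop-out. Patients are analysed as allocated, but "will be excluded from the analysis if they do not adhere to the protocol after randomisation".
- **Allocation** (Randomization and concealment): sequentially numbered, sealed opaque envelopes prepared by a third party. Whether the sequence is blocked is not stated.
- **Endpoint**: the sample size section calls 24-hour morphine consumption the primary outcome variable, whereas Outcome measures sets the primary outcome at 72 hours. The only SDs given are for 24 hours.

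**The concern.** Student's t test estimates one common variance for both groups. The protocol's own pilot figures point to a morphine-group variance nearly three times that of the methadone group. Shapiro-Wilk cannot detect this, because normal data with different spreads pass a normality check and go on to the pooled test.

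With equal group sizes, the pooled and unpooled standard errors are identical, so little is lost. With unequal sizes, the pooled standard error is too small when the more variable morphine group is the smaller one, and too large when it is the bigger one. In the first case the P value is too optimistic; in the second the test loses power. The protocol plans equal groups but does not secure them at analysis, since non-adherent patients are removed after randomisation.

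**Working it through.** **Inputs from the protocol.** SDs 8.2 and 14.0 mg; difference 30.3 − 21.5 = 8.8 mg; alpha 0.05; power 90%; 34 per group; 15% drop-out; 86 in total. **Assumptions.** Two-sided test, normal data, 24-hour SDs.

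**1. The protocol's sample size.** Average SD = √[(8.2² + 14.0²)/2] = √131.62 = 11.47 mg, so d = 8.8/11.47 = 0.767. The normal approximation gives 2 × (1.960 + 1.282)²/0.767² = 35.7, so 36 per group; the noncentral t gives 37. This is close to the stated 34 but not equal to it (a rank-test calculation with a logistic parent gives 34). The total of 86 fits 37 per group (74 × 1.15 = 85.1), not 34 (68/0.85 = 80). That mismatch is a separate matter. What counts here is that Welch's test also needs 37 per group for 90% power.

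**2. Variance ratio.** 14.0²/8.2² = 196/67.24 = 2.91. If the pilot was split 25/25, which the protocol does not say, the F test gives P = 0.011.

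**3. Standard error of the difference** (n₁ methadone, n₂ morphine).
Pooled: √{[(n₁−1)·67.24 + (n₂−1)·196]/(n₁+n₂−2) × (1/n₁ + 1/n₂)}. True: √(67.24/n₁ + 196/n₂).
- 42/31: pooled √(121.65 × 0.05607) = 2.61; true √(1.601 + 6.323) = 2.81; ratio 0.93.
- 31/42: pooled √(141.59 × 0.05607) = 2.82; true √(2.169 + 4.667) = 2.61; ratio 1.08.
- 37/37: both √(2 × 131.62/37) = 2.67; ratio 1.

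**4. Rejection rate for equal means with SDs 8.2 and 14.0** (simulation, at least 300,000 trials per split; rounded).

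| Methadone/morphine analysed | Student | Welch |
|---|---|---|
| 34/34, 37/37 or 43/43 | 5.1% | 5.0% |
| 38/35 | 5.5% | 5.0% |
| 35/38 | 4.7% | 5.0% |
| 40/33 | 6.3% | 5.0% |
| 33/40 | 4.1% | 5.0% |
| 42/31 | 6.9% | 5.0% |
| 31/42 | 3.6% | 5.0% |

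Power for 8.8 mg:
- 37/37: 90.2% (Student) and 90.0% (Welch).
- 43/43: 94.0% and 93.9%.
- 31/42: 88.6% and 91.3%.
- 40/34: 90.3% and 88.6%. Student's apparent advantage here comes with a type I error of 6.1%.

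**5. How likely is such a split?**
- *43/43 randomised, 15% lost at random.* The size difference has median 2, 95th percentile 6 and 99th percentile 9. The morphine group is smaller by 11 or more (as in 42/31) in about 0.08% of trials. Averaged over splits, Student's type I error is about 5.1%.
- *Unblocked allocation of 86 (an assumption), same loss.* The median difference is 6. The morphine group is smaller by 11 or more in about 11% of trials. The average type I error is about 5.2%, because imbalances in the two directions nearly cancel.

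**The case against.** The case for leaving the wording alone has several parts.

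- **Equal groups are planned.** This stands. At the planned sizes Student's t is nearly exact, and under balanced allocation with random loss the usual error is well under one percentage point.
- **The null is particular.** This stands. The error rates need equal means together with unequal SDs. If the two drugs acted identically, both groups would share one distribution and pooling would be valid. What remains is the standard error when methadone does work and also narrows the spread, as the pilot suggests; power, and the coverage of any interval, then depend on the split.
- **The test is conditional and the SDs are for 24 hours.** This stands as a limit. Non-normal data go to the Mann-Whitney test, and no 72-hour SD is given. But nothing in the protocol supports equal variances at 72 hours either.
- **The name may be used loosely, and an analysis plan may fix the variance option.** This is possible. Still, the protocol has named the equal-variance test, and an analysis plan that chose Welch's would depart from it.

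A reader might infer that the primary P value and confidence interval will be wrong. The documents do not support that. The distortion needs an imbalance that is not planned, nothing suggests that exclusions would fall mainly in one group, and the methods plan no confidence interval. Nor can simple randomisation be read from silence about blocking, since envelopes can be prepared in equal numbers.

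**Conclusion.** The point holds as a minor one. The named test assumes equal variances, the protocol's only variance data contradict this (ratio 2.9), and the stated normality check would not reveal it. The consequence depends on the split obtained: none to speak of with equal groups, a type I error of about 4% to 6% at moderate imbalance, and about 7% at 42/31, which is rare under balanced allocation. Averaged over random imbalances the error is about 5.1% to 5.2%, so the design as a whole is not mis-calibrated. These figures assume normal data, a two-sided test, the pilot's 24-hour SDs carrying over to the trial, and a null of equal means with unequal SDs.

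**What to change.** In Sample size calculation and statistical methods, replace Student's t test with Welch's (unequal-variance) t test for comparisons of means. If an interval for the mean difference is reported, take it from the same test. Make the change before unblinding: SPSS prints both variance lines, and naming one in advance removes a later choice between two P values.

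The cost is one phrase and about 0.1 to 0.2 percentage points of power with equal groups, with no change in the number needed (37 per group by either test). If the morphine group ends up smaller, Welch's nominal power is somewhat lower (88.6% against 90.3% at 40/34), but the difference reflects Student's inflated error rate there, not a real gain.

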Patients will be screened the day before operation for eligibility. Eligible patients will be given the patients’ information sheets regarding the main aspects of the trial. Research nurses will then discuss with the patients in light of the information provided in the information sheets. Written informed consent will be obtained from patients willing to participate in the trial. All data is collected by research team members blinded to group assignment. Patient demographics and body mass index will be recorded. The time weaned to spontaneous breathing on ASV will be recorded. At 15min after tracheal extubation and at 8h, 12h, 24h, 48h and 72h post-extubation, pain score at rest and on coughing will be quantified using Numerical Rating Scale (NRS) from 0 to 10. Zero represents no pain at all while 10 points represents the worst pain ever. The time to first morphine rescue (in minutes after surgery) will be measured. The level of sedation will be measured using the Ramsay Sedation Scale (1 = anxious, agitated or restless, or both; 2 = co-operative, oriented and tranquil; 3= respond to command only; 4 = exhibit brisk response to light glabellar tap or loud auditory stimulus; 5 = exhibit sluggish response to light glabellar tap or loud auditory stimulus; 6 = exhibits no response), episodes of nausea and vomiting, and whether antiemetics are prescribed will also be recorded at the above time points. At the same time, patients will be asked to rate the overall satisfaction with pain management on a verbal analogue scale (0 = worst possible, 100 = best possible).

The Douleur Neuropathique en 4 questionnaire (DN4)²⁶ will be used to evaluate the presence of neuropathic pain at 3 and 6 months after surgery.

The following medical and surgical data during the hospital stays will be extracted from patient charts:

1. Patient demographics (age, gender, EuroScore)
2. Type of surgery
3. Duration of surgery and duration of cardiopulmonary bypass
4. ASV time to spontaneous breathing
5. Total morphine consumption at 24 and 72 hours after surgery
6. Episodes of nausea and vomiting, and use of rescue antiemetics
7. Length of ICU and hospital stay

		STUDY PERIOD									
		Post-allocation									
TIMEPOINTS	Enrolment	Baseline	OT	4h stop sedation	15min extubate	12h extubate	24h extubate	48h extubate	72h extubate	3-month postop	6-month postop
ENROLMENT:											
Eligibility screen			X								
Informed consent			X								
Demographic data			X								

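### The normality of the trial data decides whether the primary outcome gets a t test or a Mann-Whitney test, so the primary test and effect measure are not fixed in advance

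*Protocol*

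**What the plan says.** All the analysis rules are in the Protocol section Sample size calculation and statistical methods. Summaries of continuous variables are means or medians "as appropriate after checking for normality using the Shapiro-Wilk's test". The next sentence gives Student's t test for continuous data "and by Mann-Whitney U test for non-normally distributed data". Neither sentence exempts the primary outcome, and no other section names a primary test or effect measure.

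The same section sizes the trial on consumption at 24 hours, with pilot means (SD) of "21.5 (8.2) mg in patients receiving methadone, whereas that for morphine group was 30.3 (14.0) mg". It names the software but not the test family.

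The section Primary outcomes differs on the time frame: "The primary outcome will be set at 72-hour time frame based on the postoperative morphine consumption". It gives no mean or SD for 72 hours.

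**The concern.** Morphine consumption is continuous, so the general rule governs it. The rule is stated in the protocol, so this is not a detail left open for an SAP. Under it, the shape of the observed data settles both the test and the quantity reported: a difference in mg, or a rank comparison summarised by medians.

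The two are not interchangeable. When the arms differ in spread and the data are skewed, Mann-Whitney does not test the difference in means from which the sample size was derived, and the two tests can fall on opposite sides of 0.05. A switch is plausible. A consumption total cannot be negative, and the pilot SDs are 8.2/21.5 = 38% and 14.0/30.3 = 46% of their means. At stake are a primary result whose meaning is known only after the data are in, and some power.

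**Working it through.** **Inputs from the protocol:** means 21.5 and 30.3 mg, SDs 8.2 and 14.0 mg, alpha 0.05, power 90%, 34 per arm, 86 in total (43 per arm). **Assumptions:** two-sided test; distribution shape (normal, gamma or lognormal); rule read as Mann-Whitney if Shapiro-Wilk p < 0.05 in either arm, otherwise Student's t.

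**1. The stated 34 per arm.** Difference = 30.3 − 21.5 = 8.8 mg. SD = √((8.2² + 14.0²)/2) = 11.47 mg. d = 8.8/11.47 = 0.767.

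- Normal approximation: n = 2(1.960 + 1.282)²/0.767² = 35.7, so 36 per arm. The exact t test needs 37. Power of the t test at 34 is 87.6%.
- Mann-Whitney by asymptotic relative efficiency (ARE) with a logistic parent (ARE = π²/9 = 1.097): 34 patients count as 34 × 1.097 = 37.3, giving 90.5% power. The required number is exactly 34.
- Mann-Whitney with a normal parent needs 39 per arm; with the minimum ARE it needs 43.

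Every variant takes d from the means and SDs. The stated 34 is close to the t test result but matches the logistic Mann-Whitney option exactly, so the sizing test cannot be identified.

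**2. Power with the pilot means and SDs.** 10,000 simulated trials per row; Monte Carlo error about 0.2 to 0.4 points.

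| Shape | n per arm | Mann-Whitney chosen | Power, rule | Power, Welch | Loss (points) |
|---|---|---|---|---|---|
| Normal | 34 | 9.8% | 87.1% | 87.3% | 0.1 |
| Gamma | 34 | 62.1% | 83.6% | 89.3% | 5.7 |
| Lognormal | 34 | 86.1% | 87.1% | 90.8% | 3.7 |
| Normal | 43 | 9.3% | 94.0% | 94.2% | 0.2 |
| Gamma | 43 | 72.0% | 91.2% | 95.4% | 4.2 |
| Lognormal | 43 | 93.2% | 93.6% | 96.3% | 2.7 |

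Repeat runs of the gamma row at 34 gave losses of 5.0 to 5.7 points, so I take about 5.5. The t test and Mann-Whitney disagreed on significance in about 4% to 9% of trials. Applying Shapiro-Wilk to pooled residuals instead gives much the same power under skew: 84.8% and 86.8% at 34 per arm (gamma, lognormal), 91.1% and 93.5% at 43.

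**3. Power with a common coefficient of variation** (0.38 or 0.46 in both arms), rule minus Welch:

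- Gamma, n = 34: 94.5 − 95.5 = −1.0; 82.5 − 84.8 = −2.3. n = 43: 97.6 − 98.3 = −0.7; 90.4 − 92.5 = −2.1.
- Lognormal, n = 34: 95.3 − 95.0 = +0.3; 86.5 − 85.0 = +1.5. n = 43: 98.5 − 98.3 = +0.2; 93.3 − 92.4 = +0.9.

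**4. No difference between arms.**

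- Identical distributions (coefficient of variation 0.38 or 0.46): the rule rejects in 4.8% to 5.5%.
- Equal means of (21.5 + 30.3)/2 = 25.9 mg but SDs 8.2 and 14.0: normal, 5.0% and 5.4% at 34 and 43 per arm; gamma, 9.1% and 10.4%; lognormal, 12.2% and 13.8%. Welch gives 4.7% to 5.2% and Student's t 4.9% to 5.3%.
- In the skewed cases, rejections favouring methadone are only 0.4% to 1.2%, below the nominal 2.5% per side. The other 7.9% to 13.4% favour morphine, the wider arm.

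**The case against.** The strongest reply is that the rule is written in advance and turns on distribution shape, not on a p-value or on anyone's discretion. That is right. A reader might infer that the investigators could pick the favourable test, or that the rule inflates false claims for methadone. The protocol supports neither, and step 4 contradicts the second.

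A reader might also infer that the trial was definitely sized for a t test, so that any rank test contradicts the plan. That goes too far. No sizing test is named, and 34 per arm fits a logistic Mann-Whitney calculation better than a t test. What remains is that the inputs are means and SDs, and that the analysis is not tied to one test under either reading.

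Further limits are fair:

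- The protocol attaches Shapiro-Wilk to the choice of summary statistics. The test sentence names no criterion or cut-off, and whether normality is checked by arm is not stated.
- The skew is assumed; only means and SDs are given.
- The equal-means case with unequal SDs is a stress case. The two distributions differ there, so a rank test that rejects is not wrong on its own hypothesis.
- Discordance between the tests does not itself measure harm: with normal data they disagree in over 5% of trials at 34 per arm, yet power barely changes.

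These points limit the size of the problem. They do not supply a fixed primary test.

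**Conclusion.** The point holds: the stated rule leaves the primary test and effect measure to the data. It should be changed, but it is minor to moderate in effect. Against Welch's test the cost in power is essentially nil if the data are normal, about 3 to 5.5 points if they are skewed with the pilot SDs, and between 2.3 points lower and 1.5 points higher under a common coefficient of variation. Type I error is about 5% when the arms are identical. The main gain from a change is a primary result with one meaning set beforehand.

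The sizes rest on the assumed shapes, the assumed switching rule and a two-sided 5% level. They apply to 24 hours only. The sample-size section calls consumption at 24 hours the primary variable ("based on postoperative morphine consumption at 24 hours, which is the primary outcome variable"), whereas Primary outcomes sets 72 hours. No size can be given for 72 hours from the protocol.

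**What to change.** Name one primary analysis that applies whatever the normality check shows: the difference between arms in mean morphine consumption (mg), with a 95% CI and unequal-variance standard errors. Keep Mann-Whitney as a sensitivity analysis. State which test the sample size was computed for. The wording serves whichever time frame is settled as primary, because Data collection already plans "Total morphine consumption at 24 and 72 hours after surgery".

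Optionally, adjust for a few prespecified baseline variables the protocol already records, such as age, BMI and type of surgery ("Patient demographics and body mass index will be recorded"). This is for precision only and is not needed to cure the defect. The gain depends on an R² that the protocol does not give. Replacing d by d/√(1 − R²), assumed values of 0, 0.10 and 0.20 give power at 34 per arm of 87.6%, 90.7% and 93.6%.

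The cost is wording, with no new data. There are two downsides. A few high users can pull a mean, which the sensitivity analysis would show. If the data are lognormal with a common coefficient of variation, the present rule would have had 0.2 to 1.5 points more power.
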